A final consideration in the determination of the sample size for the proposed study was the necessary sample size for stable and precise estimates of treatment effects using multilevel modeling. Maas and Hox's (2005)¹¹³ canonical work on necessary sample sizes for group level effects in MLM determines that group sizes of 20 members and larger is sufficient for generating unbiased estimates. Given that primary questions center on treatment effects in the proposed study, 20 couples per treatment ensures an adequate sample size for generating unbiased estimates of treatment effects thus permitting use of MLM to test study hypotheses.

Analysis Plan

Aim 2

Both primary outcomes will be analyzed using a two-level MLMs as described by the following series of equations:

$$\text{Level-1: } Y(\text{Adherence})_{ij} = \beta_{0j} + e_{ij}$$

$$\text{Level-2: } \beta_{0j} = \pi_{0j} + \pi_{0[1 \text{ to } n]} * [\text{covariates determined by tests of between group differences at baseline in demographic and sleep variables}] + \pi_{0[n+1]} * [\text{Treatment}] + \mu_{0j}$$

where i represents daily measures total hours of CPAP use/whether total hours of CPAP ≥ 4 hours (0 = no, 1 = yes) over the 3 month follow-up and j represents individuals. Treatment is a dummy coded variable with 0 = IC and 1 = We-PAP. The level two intercept in this model, π_{0j} , represents the maximum likelihood estimate of average adherence and $\pi_{0[n+1]}$ provides a test of the primary study hypotheses. Separate models will be run for total hours of sleep and ≥ 4 hours of CPAP use as outcomes estimated using models with Gaussian and binomial distributions respectively.

Secondary outcomes will be analyzed using a three-level MLMs as described by the following series of equations:

$$\text{Level-1: } Y(\text{Outcome})_{ijk} = \beta_{0jk} + \beta_{1jk} * (\text{Pre vs. 3 month follow-up}) + e_{ijk}$$

$$\text{Level-2: } \beta_{0jk} = \pi_{00k} + \pi_{0[1 \text{ to } n]k} * [\text{covariates determined by tests of between group differences at baseline in demographic and sleep variables}] + \pi_{0[n+1]k} * (\text{Patient vs. partner}) + \mu_{0jk}$$

$$\beta_{1jk} = \pi_{1jk} + \pi_{1[n+1]k} * (\text{Patient vs. partner})$$

$$\text{Level-3: } \pi_{0jk} = \gamma_{000} + \gamma_{001} * [\text{Treatment}] + r_{00k}$$

$$\pi_{1jk} = \gamma_{100} + \gamma_{101} * [\text{Treatment}]$$

$$\pi_{1[n+1]k} = \gamma_{1[n+1]0} + \gamma_{1[n+1]1} * [\text{Treatment}]$$

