where i represents repeated measurement of the outcome variable, j represents individuals, and k represents couples. Treatment is a dummy coded variable with 0 = IC and 1 = We-PAP; Pre vs. 3 month follow-up is a dummy coded variable with 0 = pre-treatment and 1 = 3 month follow-up; and, patient vs. partner is a dummy coded variable with 0 = patient and 1 = partner. The level three intercept in this model, π_{0jk} , represents the maximum likelihood estimate of average outcome, π_{1jk} provides a test of differential treatment effects, and $\pi_{1[n+1]k}$ provides a test of whether these effects differ for patients and partners. Separate models will be run for each outcome.

Missing Data. Mechanisms of missingness will be evaluated in outcomes and potential mediators with missing data. If missingness patterns are consistent with MAR assumptions, recently developed fully conditional specification with chained equations methods for multiple imputation of missing data in MLMs will be used to handle missing data^{114,115}. All variables in hypothesis tests plus additional auxiliary variables will be included; potential auxiliary variables will be carefully screened using methods recommended for small sample sizes¹⁰³. If missingness patterns are consistent with MNAR assumptions, we will consider the use of pattern mixture models¹⁰⁴ and conditionally dependent dropout¹¹⁶ models to minimize any potential bias in estimation of treatment effects.

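### For secondary outcomes the SAP names arm-specific changes (`π_1jk`, `π_1[n+1]k`) as the treatment tests, when its own equations make the Treatment coefficients inside them (`γ_101`, `γ_1[n+1]1`) the between-arm tests

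*SAP*

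**What the plan says.** The model for secondary outcomes is in SAP 4.4, Analysis Plan, Aim 2. In compact form:

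- Level 1: outcome = `β_0jk + β_1jk` × time + error
- Level 2 (slope): `β_1jk = π_1jk + π_1[n+1]k` × role
- Level 3 (slopes): `π_1jk = γ_100 + γ_101` × Treatment, and `π_1[n+1]k = γ_1[n+1]0 + γ_1[n+1]1` × Treatment

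The coding follows the equations. For treatment: "Treatment is a dummy coded variable with 0 = IC and 1 = We-PAP; Pre vs. 3 month follow-up is a dummy coded variable". Time is coded "with 0 = pre-treatment and 1 = 3 month follow-up". For role: "patient vs. partner is a dummy coded variable with 0 = patient and 1 = partner".

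The SAP then assigns the tests. It says `π_1jk` "provides a test of differential treatment effects" and `π_1[n+1]k` "provides a test of whether these effects differ for patients and partners". No sentence names `γ_101` or `γ_1[n+1]1` as a tested coefficient. For the primary adherence model, by contrast, the SAP names `π_0[n+1]`, which is the coefficient of Treatment itself.

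**The concern.** An analysis plan should fix in advance which coefficient carries each hypothesis. Here the one statement that does so for the secondary outcomes points to quantities that include the IC arm's own change. An analyst who looks for `π_1jk` and `π_1[n+1]k` in fitted output would be led to the time and time-by-role terms. The terms needed are time-by-treatment and time-by-role-by-treatment.

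This matters because of the design. Baseline precedes PAP initiation and patients in both arms intend to start PAP (Protocol, section 1 and Inclusion Criteria). The Protocol's Background links PAP use to better sleepiness and cognition. Some improvement in both arms is therefore plausible for at least part of the secondary outcomes, and the statement applies to each of them because every outcome gets its own model of this form.

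**Working it through.** **1. What the SAP powered.** The SAP states power of .8 or higher for a between-group d = .54, with 20 couples per arm and within-couple r = .3. Take the couple mean as the unit, so that its SD is √((1 + 0.3)/2) = √0.65 = 0.806. The noncentrality is 0.54 / (0.806 × √(2/20)) = 2.118. At one-sided α = 0.10 (SAP, General considerations) power is Φ(2.118 − 1.282) = 0.799, or 0.792 with the noncentral t. The figure is reproduced to rounding as a comparison between arms.

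**2. Substitution.** Putting Levels 2 and 3 into Level 1, with the SAP's coding, gives these expected changes from baseline to 3 months:

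| | Patient (0) | Partner (1) | Partner minus patient |
|---|---|---|---|
| IC (0) | `γ_100` | `γ_100 + γ_1[n+1]0` | `γ_1[n+1]0` |
| We-PAP (1) | `γ_100 + γ_101` | `γ_100 + γ_101 + γ_1[n+1]0 + γ_1[n+1]1` | `γ_1[n+1]0 + γ_1[n+1]1` |
| We-PAP minus IC | `γ_101` | `γ_101 + γ_1[n+1]1` | `γ_1[n+1]1` |

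`π_1jk` is the patient column within one arm, and `π_1[n+1]k` is the last column within one arm. Neither is a contrast between arms. The contrasts are in the bottom row.

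**3. Size for `π_1jk`, if its intercept were tested.** Assumptions that are not in the documents: no treatment effect, the same improvement δ in both arms, unit SD at each visit, and pre-post correlation ρ. From the SAP: one-sided α = 0.10 and 20 patients per arm.

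- SD of change = √(2(1 − ρ)), which is 1.000 at ρ = 0.5 and 0.775 at ρ = 0.7.
- Noncentrality = δ√n / SD of change. With δ = 0.3 and n = 20 it is 0.3 × 4.472 / 1.000 = 1.342, and 0.3 × 4.472 / 0.775 = 1.732.
- The critical t on 19 df is 1.328. Rejection probability is 51% at ρ = 0.5 and 66% at ρ = 0.7.

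With δ = 0.5 the same steps give 82% and 94%. At the lower correlation ρ = 0.3 the figures are 43% (δ = 0.3) and 71% (δ = 0.5). In simulation (20,000 runs per setting), the test of `γ_101` rejected in about 10% of trials in every one of these settings.

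**4. Size for `π_1[n+1]k`.** If patients and partners improve equally, `γ_1[n+1]0` is zero and its test rejects in about 10% of trials, as it should. The term misleads only when there is a gap between roles that both arms share. Suppose patients improve 0.5 SD more than partners in both arms, and test two-sided at 0.10, because the SAP gives no direction. The standard error is √(4(1 − ρ)/20), which is 0.374, 0.316 and 0.245 at ρ = 0.3, 0.5 and 0.7. Testing `γ_1[n+1]0` then rejects in 38%, 48% and 65% of trials. Testing `γ_1[n+1]1` rejects in about 10%.

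**5. Model fit.** One mixed model was fitted to a large simulated data set (400 couples) with no treatment effect and a true change of 0.5 in patients and 0.2 in partners. The time term was 0.525 (p < 0.001) and time × role −0.360 (p < 0.001). Time × treatment was −0.025 (p = 0.54) and time × role × treatment 0.018 (p = 0.74). Only the last two answer the trial's questions, and both were correctly null.

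**The case against.** The strongest reply is that this is loose notation and the intent is clear. The SAP calls the tested quantity a differential treatment effect, and its sample-size section uses the same term for CBT against IC and powers the secondary outcomes for between-group differences. The same sentence also labels `π_0jk` the level-three intercept, although that intercept is `γ_000`, so all three Level-3 rows may simply be named by their left-hand side. Moreover, `π_1jk` takes a different value in each arm, so there is no single test of it. Any error rate requires the reader to choose an interpretation. All of this stands, and it limits the point to which coefficient is named. The model structure is sound and yields the right contrasts directly. What the reply does not do is supply the missing statement: nothing in the documents says that the symbols are shorthand.

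Three stronger readings are tempting and are not supported:

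- *That shared improvement contaminates both named terms.* It enters through `π_1jk`. Improvement equal in the two roles cancels in `π_1[n+1]k`.
- *That the rejection rates above are this trial's type I error.* They hold only if the IC change is itself reported as the We-PAP effect, and only under an assumed improvement and correlation.
- *That every secondary outcome would show a false effect.* The documents give no expected IC change for outcomes such as relationship quality or partner measures, and the Protocol's Background cites non-adherence of up to 80%, which weakens any presumption of uniform improvement.

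**Conclusion.** The statement is wrong as written and should be corrected, but it is a correction of labels and not of the model. That `π_1jk` and `π_1[n+1]k` are within-arm quantities follows from the SAP's own equations and coding and needs no assumption. The consequence is conditional on a literal reading. In that case a 0.3 SD improvement shared by both arms would be declared a treatment effect in 51–66% of trials at a nominal 10% (ρ = 0.5 to 0.7). Those inputs are assumed and the figures only illustrate size.

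A reader might infer that the decision to proceed to a larger trial is at risk. It is not: the SAP ties the go/no-go threshold to the primary adherence outcomes, and for those it names the Treatment coefficient correctly.

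**What to change.** In SAP 4.4, Analysis Plan, Aim 2, replace the assignment of tests that follows the three-level equations with wording to this effect:

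- `γ_101` tests the differential treatment effect in patients (role coded 0 = patient).
- `γ_101 + γ_1[n+1]1` is the corresponding treatment effect in partners.
- `γ_1[n+1]1` tests whether the treatment effect differs between patients and partners.
- `γ_100` and `γ_1[n+1]0` describe change in the IC arm only and are not treatment tests.

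The qualification to patients is needed. With this coding `γ_101` alone says nothing about partners, whereas the SAP's power figure for these outcomes uses both members of the couple.

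The cost is one reworded statement. The model, sample size, data collection and primary analysis do not change.
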